4.3 Device Purchase and Interpretation

The investigator and co-investigators have met with industry to purchase the SpiderFlash devices for specific use in this study. A reduced price for 10 SpiderFlash devices (\$1150.00) was negotiated and the devices have been purchased, with delivery expected in May 2017.

SpiderFlash device interpretation will be performed initially by technicians that are working with the software for other clinical services. Technician interpretation of the SpiderFlash will be overseen by Operations Manager, [name]. Technician reports

are subsequently reviewed by the investigator and co-investigator, blinded to patient demographics and details. All reports will be sent to the primary cardiologist for all enrolled patients.

4.4 Potential Issues and Mitigating Strategies

- Patients may develop AF in-hospital and revert to sinus rhythm prior to discharge: these patients are excluded (AF already diagnosed, no role for intensive monitoring as per primary outcome).
- 2) Impact on anticoagulation: all test results will be communicated with the primary cardiologist and family physician. This study does not prescribe anticoagulation and will not influence the prescribing physicians- rather, all information will be communicated to the primary cardiologist or family physician.
- 3) Impact on stroke: this pilot study allows for the planning of a subsequent intervention with cardiovascular endpoints.

4.5 CCS-Bayer Resident Vascular Award and Funding

This project is co-led by a trainee (CC) and received full funding and won first prize at the CCS-Bayer Resident Vascular Award trainee competition in October 2016, receiving \$30,000 funding (\$20,000 + \$10,000 presentation bonus). There is significant motivation to support this project from a local and divisional level, including commitment from various faculty and research staff at Vancouver General Hospital.

4.6 Research Infrastructure

The coordinating centre is the UBC Division of Cardiology, Cardiology Research at Vancouver General Hospital (located at Gordon and Leslie Diamond Health Care Centre). This research project will be performed at two sites in British Columbia with supervisors at each site (Vancouver General Hospital: JA, KG; St. Paul's Hospital: AK, MD). Each site benefits from a large referral base for STEMI and NSTEACS from across the province. There is established research support for the screening and enrollment of patients (research nurses are supportive). This project is financially supported by the UBC Division of Cardiology, with divisional research funds (CAPP) to support the purchase and donation of 10 Spiderflash monitors to this project.

The steering committee includes the principal investigator and co-investigators listed in this application. Enrollment will be performed by the Cardiology Research staff (AS, JC) and trainee (CC). The endpoint adjudication committee will be attend through consensus of the principal investigator (JA) and trainee (CC). The data management team will include the co-investigator (AS) with expertise in data management and RedCap Database development and the trainee (CC).

The trainee (CC) leading this project has significant research experience, and has participated in multiple prospective and retrospective projects in the field. He has written a review of loop recorders in syncope, and is writing a review of novel technologies for detecting AF. He has received multiple awards, including from the Canadian Stroke Prevention Intervention Network (C-SPIN) and the Cardiac Arrhythmia Network of Canada (CANet), and twice attended the C-SPIN Annual Clinical Trials workshop. The

supporting mentor and supervisors have extensive experience in clinical trials and AF research, and the trainee has collaborated with them on various occasions. Together, these supports and experiences provide an exceptional research environment for the design, coordination, and completion of this research project.

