3.7 Methods

Upon enrollment, patients will be randomized (2:1 distribution for intensive monitoring, stratified by STEMI vs. NSTEACS) to receive standard care or intensive monitoring. Intensive monitoring entails wearing a Spiderflash (LivaNova) 30-day external cardiac monitor at discharge. A 30-day external cardiac monitor represents the most feasible, high-quality, non-invasive monitoring strategy possible, while maximizing the duration of uninterrupted monitoring beginning at discharge. Demographics, clinical characteristics, and risk factors for stroke and bleeding (i.e. CHADS₂, HASBLED) will also be collected at enrollment.

The research team will perform all aspects of SpiderFlash data acquisition and interpretation. The research team has purchased the SpiderFlash devices and the programming/analysis software. After patients have completed the 30-day recording, the information will be downloaded directly off the device (via SD card). There is no

industry involvement and no data transfer to a server or out of country. There is no relationship between the SpiderFlash provider and UBC/VCH, and no connection between the research team and SpiderFlash provider. All funds are provided by a research award attained by the trainee (CC).

Spiderflash ECGs will be interpreted by the trainee (CC, cardiology resident) with oversight from the supervising physician (JA). The reports will be distributed to the primary cardiologist and family physician. The standard care strategy includes a 12-lead ECG performed prior to discharge and at follow-up with the primary cardiologist (typically 4-8 weeks post-MI).

Cardiac medication review will be performed by the trainee (CC) at 90-days and 1-year post-monitoring (to allow adequate time for anticoagulant initiation). A telephone follow-up (15 min) and chart review will confirm anticoagulation status, and reasons for initiating or withholding anticoagulation.

Both the intensive monitoring and control groups will receive telephone follow-up at 90days to assess prescription status. No additional care or clinic visits are scheduled for the control group. All additional data (including ECGs performed by primary cardiologist and confirmation of anticoagulation status) in the intervention and control group will be performed via electronic chart review of Cardiology EMR.

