3.8 Sample Size Calculations and Statistical Analysis

Previous retrospective and cohort data has identified new-onset AF in 7-14% of patients in-hospital or within 2 days after MI.^{4, 21} Between 3-30 days, new AF occurs in 3.7% when ascertained through an electronic ECG database, with the remainder of AF (12%) developing during long-term follow-up (6.6 years).²¹ Thus, at 30-days post-MI, we anticipate that the standard care strategy will detect similar rates of AF to this cohort study (3.7%).

Using an ILR, new-onset AF was detected in 16% at 2-months (approx. 8% at 1-month, CARISMA).⁵ However, in the CARISMA study, AF was only detected when HR \geq 125 bpm, effectively missing AF at slower rates (<125 bpm).⁵ Up to half of patients (49%) with AF post-MI have heart rates \leq 94 bpm.⁷ Thus, we anticipate that an intensive monitoring strategy (30-day external cardiac monitor) will detect higher rates of AF (16%) after 30-days (double ILR rate given the heart rate limitations).

With a 2:1 randomization to intensive monitoring and using a 5% significance level (α =0.05), **216 patients** (144 patients with intensive monitoring and 72 patients with standard care) are required to have a 80% power (1- β =0.80) of detecting an increase in new AF (primary outcome) from 3.7% (standard care) to 16% (intensive monitoring). Accounting for a 5% drop-out, the final sample size is **240 patients (120 patients per group)**.

Statistical analysis will be performed using an intention-to-treat analysis for patients randomized to the intensive monitoring or standard care strategy. Regression analysis

will be used to compare rates of AF at 30-days between both groups. Time-to-event analysis will be used to compare the time to development of AF in both groups.

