4. FEASIBILITY

4.1 Recruitment

There are approximately 310 STEMI/year in the health region (308-341/year, regional data²²) with at least 4 NSTEACS per 1 STEMI (1240 NSTEACS/year, including transfers, regional data²³). Patients will be excluded based on LVEF>40% (66% ineligible²⁴), pre-existing AF (9%²¹), in-hospital AF (14%⁴), LV thrombus (8%²⁵), and other factors (i.e. heart valves/VTE; uncommon, $\leq 1\%^{26}$). 368 patients/year will meet enrollment eligibility. Using an enrollment rate of 66%, 20 patients will be enrolled per month (10 for intensive) and the target (264 patients) will be met in 13 months.

Patient recruitment will be overseen by Cardiology Research Manager, [name], and Cardiology Clinical Research Coordinator, [name].

Patients will be recruited directly from the Vancouver General Hospital Coronary Care Unit (CCU). The Cardiology research nurses ([name] and [name]) routinely screen patients admitted to the CCU for study eligibility. This process is well-established for a number of ongoing studies that operate in the CCU.

In this study, prospective participants will be identified upon admission to the CCU meeting the eligibility criteria. Study participants will be approached by [name] and [name] for consent to participate in the study.

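### Post-discharge ECGs come only from the Cardiology EMR although referral is province-wide, so AF documented elsewhere may be missed, mainly in controls

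*Combined protocol and SAP*

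**What the plan says.** **Source of ECG data.** Section 3.7 gives controls no study visit and no study ECG after discharge. Their only planned post-discharge ECG is the one at usual cardiologist follow-up, typically 4 to 8 weeks after the MI. For both arms, that ECG and other additional data "will be performed via electronic chart review of Cardiology EMR". Retrieval of ECGs held elsewhere is not described.

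**Recorder data.** The same section has the research team download the recording from the device's SD card, so recorder AF does not pass through the EMR.

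**Where patients come from.** Section 4.6 states: "Each site benefits from a large referral base for STEMI and NSTEACS from across the province". Section 4.1 counts "1240 NSTEACS/year, including transfers" in the recruitment pool.

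**Other routes to an AF diagnosis.** The follow-up form (Appendix 2, used at 3 months and 1 year) has an AF item marked as patient-reported, and items on anticoagulant use, re-hospitalization and emergency visits. The AF item has no field for an ECG date, place or confirmation. Section 3.7 gives prescription status as the purpose of the 90-day call to both arms.

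**Planned comparison.** Section 3.8 compares 30-day AF rates by intention to treat, expecting 3.7% under standard care and 16% with monitoring. The 3.7% comes from a cohort whose AF was ascertained through an electronic ECG database.

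**The concern.** The two arms depend on the EMR to different degrees. In the monitored arm the recorder is the main source of AF. In the control arm the main ECG-based source is whatever the Cardiology EMR holds. A patient who returns home and is followed elsewhere may have AF documented on an ECG that the study never sees, and the plan would then read an empty chart as no AF. A gap in EMR coverage therefore removes mostly control events, which pushes the rate difference and ratio toward monitoring.

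Few control events are expected, so each one carries weight. The planned control rate also presumes ECG capture like that of the source cohort, and a narrower record would yield a lower rate. Section 4.4 describes the study as a pilot for a later trial, so an understated control rate would carry into that design.

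**Working it through.** **Inputs**
- Control rate 3.7%, monitored rate 16%, two-group comparison at 5% with 80% power, 144 monitored and 72 control (section 3.8). Sidedness is not stated; two-sided is used here.
- f: the share of control AF recorded only outside the EMR and not recovered by another route. **This is an assumption.** The documents do not say which clinics the EMR covers or what share of patients is followed elsewhere, so a range is shown. If all AF is lost among patients followed outside, and they have the same AF rate as the rest, f equals the share followed outside.

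**1. The plan's own figure**

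Pooled rate at 2:1 = (0.037 + 2 × 0.16)/3 = 0.119.

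Controls needed = [1.96 × √(1.5 × 0.119 × 0.881) + 0.8416 × √(0.037 × 0.963 + 0.16 × 0.84/2)]² / 0.123² = (1.047/0.123)² = 72.5, rounded up to 73.

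Total = 73 + 146 = 219, against the stated 216. Power at 72 and 144 is 79.7%, so the stated size reproduces closely.

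**2. Effect of lost control AF**

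Observed control rate = 3.7% × (1 − f). Inflation of the difference = 3.7 × f points. Ratio = 16 / [3.7 × (1 − f)]. Control events lost = 72 × 0.037 × f. The monitored rate is held at 16%.

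| f | Control rate | Difference (points) | Inflation (points) | Ratio | Events lost of 72 |
|---|---|---|---|---|---|
| 0 | 3.7% | 12.3 | 0 | 4.3 | 0 |
| 20% | 3.0% | 13.0 | 0.7 | 5.4 | 0.5 |
| 25% | 2.8% | 13.2 | 0.9 | 5.8 | 0.7 |
| 50% | 1.85% | 14.2 | 1.9 | 8.6 | 1.3 |
| 100% | 0% | 16.0 | 3.7 | undefined | 2.7 |

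The difference moves little because the control rate is small. The ratio moves a lot for the same reason.

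**3. Effect on a significance test** (uncorrected chi-square)

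Expected counts are 144 × 0.16 = 23 and 72 × 0.037 = 2.7, about 3.

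| Monitored | Control | p |
|---|---|---|
| 23/144 | 3/72 | 0.012 |
| 23/144 | 4/72 | 0.029 |
| 23/144 | 5/72 | 0.063 |
| 18/144 | 2/72 | 0.020 |
| 18/144 | 3/72 | 0.051 |
| 18/144 | 4/72 | 0.11 |

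At the planned counts, restoring one missed control event leaves the result significant; restoring two does not. If the monitored arm yields 18 events (12.5%, below plan), one control event decides which side of 0.05 the result falls on.

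These counts use 144 and 72. Sections 3.8 and 4.2 also give 120 per group and 1:1 allocation, a conflict to be settled separately. With 120 per group, 19/120 against 5/120 gives p = 0.003, so single events matter less.

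**The case against.** **The premise is an inference.** A wide referral base describes where patients come from, not where they are followed. Section 4.1 builds its recruitment estimate from regional figures, and counting transfers does not show follow-up outside the network. This stands. A reader might infer that control AF *is* missed; the documents support only that it *may* be.

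**The EMR is not the only route.** A patient told of AF by an outside physician could report it on the follow-up form, and a new anticoagulant or an admission could reveal it. Section 1.1 says more than 90% of patients in two implanted-monitor studies were unaware of their AF, but that concerns silent AF rather than a clinician's diagnosis. This stands in part: the routes would lower f, but the AF item has no ECG behind it and cannot confirm 30 seconds or the date.

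**The loss might not run one way.** The SD card has to come back to the research team, and no return procedure for distant patients is described. Unreturned devices would cost monitored-arm events. So the loss falls mainly, not exclusively, on controls.

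**The larger endpoint problems lie elsewhere.** Section 3.6 words the primary outcome as AF detected by the external recorder, which controls do not wear, and the 4 to 8 week ECG falls mostly after day 30. Both points are correct and need their own resolution. They limit what retrieval can add at 30 days but do not remove the need for it: the 3.7% control rate in section 3.8 makes sense only if AF found without the recorder counts.

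**A control with no ECG is not missing data.** This stands in full. In a comparison of strategies, that patient is a true non-detection. Excluding such controls would be a one-arm, post-randomisation exclusion.

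**Conclusion.** The weakness is real and moderate in size. Section 3.7 confines ECG collection to one record system, the referral base is province-wide, and the arm without a recorder depends most on that system. The likely direction of bias is toward monitoring.

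On the plan's own rates the inflation cannot exceed 3.7 points. A reader might infer from the steep rise in the ratio that incomplete capture could produce the trial's result by itself. It could not: with no loss at all, the expected difference is still 12.3 points. Nor do single events generally decide the outcome; that holds when the monitored rate falls short of plan or the control count runs above it. What is at risk is the size of the ratio, the reading of a borderline result, and the control rate handed to the next trial.

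This rests on two assumptions: some follow-up takes place outside the EMR, and the form's other items do not fully recover the AF found there. The documents settle neither.

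**What to change.** In section 3.7:

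1. On the 90-day call already made to both arms, ask the date and place of every post-discharge ECG, rhythm monitor or AF diagnosis.
2. In both arms, request the record from the treating cardiologist, family physician or hospital when it is not in the EMR. Section 4.3 already sets up correspondence ("All reports will be sent to the primary cardiologist for all enrolled patients"), but controls generate no recorder report, so their physicians' details may have to be collected at enrolment.
3. Verify patient-reported AF against the tracing and its date. Count it in the 30-day comparison only if it falls within the window.
4. Report, by arm, the share of patients followed outside the EMR.

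In section 3.8, keep all randomised patients in the intention-to-treat comparison and treat a control who truly had no ECG as AF not detected. Limit the sensitivity analysis to patients who report an outside ECG that could not be obtained.

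The cost is a few questions on an existing call and staff time for the record requests. The reported difference may become slightly less favourable to monitoring. No extra patients or visits are needed.

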3.6 Outcomes

- Primary Outcome: development of atrial fibrillation or flutter lasting ≥30 seconds (consensus definition^{19, 20}) detected using external loop recorder
- 2) Secondary Outcome: anticoagulation prescription, AF-related hospitalization, and a composite secondary outcome of all-cause hospitalization, re-infarction, stroke, and death at 90-days and 1-year after completion of monitoring

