4.2 Randomization and Blinding

Patients will be recruited from the Vancouver General Hospital Cardiac Care Unit (CCU) and St. Paul's Hospital Cardiac Intensive Care Unit (CICU). Randomization will be performed using a central randomization system (integration through RedCap) in a 1:1 manner, and will be implemented using an online access (RedCap) system. A back-up randomization will be available through sealed envelope in case of database issues. The allocation sequence will be generated by the co-investigator and Database expert (AS). Patients will not be blinded to the monitoring device. Physicians will blinded to patient identity, but will only review results for patients that received the monitoring device.

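### AF-related hospitalization has no criterion and no masked adjudication, so the same admission can more readily be labelled AF-related in the monitored arm

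*Combined protocol and SAP*

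**What the plan says.** Section 3.6 gives the secondary outcomes, at 90 days and 1 year after monitoring, as "anticoagulation prescription, AF-related hospitalization, and a composite secondary outcome of all-cause hospitalization, re-infarction, stroke, and death". It does not define AF-related.

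Section 4.6 covers adjudication: "The endpoint adjudication committee will be attend through consensus of the principal investigator" and the trainee. It does not list the endpoints to be adjudicated.

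The same people have other roles:
- **Reading.** Section 3.7 says "Spiderflash ECGs will be interpreted by the trainee", overseen by the supervising physician, whose initials match those of the principal investigator in 4.6. Section 4.3 adds a first read by technicians, whose reports "are subsequently reviewed by the investigator and co-investigator, blinded to patient demographics and details".
- **Enrolment.** Section 4.6 says "Enrollment will be performed by the Cardiology Research staff" and, in the same sentence, the trainee.
- **Follow-up.** Section 3.7 says "Cardiac medication review will be performed by the trainee" at 90 days and 1 year, using telephone and chart review.
- **Data entry.** Section 4.7 assigns it to the principal investigator and co-investigators, including the trainee.

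Section 4.2 leaves patients unblinded and adds: "Physicians will blinded to patient identity, but will only review results for patients that received the monitoring device". On results, section 3.7 says "The reports will be distributed to the primary cardiologist and family physician"; sections 4.3 and 4.4 agree.

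**The concern.** Whether an admission is AF-related depends partly on whether AF is already known. A monitored patient admitted with breathlessness or heart failure may arrive with AF found by the recorder. A control with the same undetected arrhythmia and the same admission would not. Without a written criterion, the label can follow prior knowledge of AF instead of what happened during the admission.

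The adjudicators are not shielded from that knowledge. The masking in 4.2 and 4.3 applies to reading recordings, which exist in one arm only, and does not extend to judging clinical events. The trainee may know the arm from enrolment, reading or follow-up, and the 3-month form in Appendix 2 carries device questions meant for the monitored arm.

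Section 4.4 describes this as a pilot for planning a later trial with cardiovascular endpoints. An AF-related admission rate that differs by arm because of labelling would be a poor input to that plan.

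**Working it through.** **Plan's own figure.** The plan gives no rate for AF-related hospitalization. Its AF detection rates (3.8) are 3.7% for standard care and 16% for intensive monitoring. As a check that these are the design rates: a two-proportion calculation at 2:1, two-sided alpha 0.05 (sidedness assumed), 80% power and no continuity correction gives 73 + 146 = 219, against the stated 216. Power at 72 and 144 is 79.7%.

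**Arm sizes.** The total is 240 (3.8). Allocation is 2:1 in 3.7 and in the power statement of 3.8, but 120 per group later in 3.8 and 1:1 in 4.2. Both 80 v 160 and 120 v 120 are carried.

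**Assumptions, not in the documents.**
- r = one-year admission rate, 20-30%, equal in both arms and unrelated to AF status.
- q = chance that an admission is labelled AF-related when AF is known, 25-75%, equal in both arms.
- q0 = the same chance when AF is not known, 2%.
- Known AF stays at the 30-day values.

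**Formula.** With a = share with known AF, labelled rate = r × [a × q + (1 − a) × q0]. The ratio of arms is [0.16q + 0.84q0] / [0.037q + 0.963q0]; r cancels.

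**Upper bound.** With q0 = 0 the ratio is 0.16 / 0.037 = 4.3. Any background labelling lowers it, and it reaches 1 when q0 = q.

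**With q0 = 2%.**
- q = 25%: (0.0400 + 0.0168) / (0.00925 + 0.01926) = 0.0568 / 0.02851 = 1.99
- q = 50%: (0.0800 + 0.0168) / (0.0185 + 0.01926) = 0.0968 / 0.03776 = 2.56
- q = 75%: (0.1200 + 0.0168) / (0.02775 + 0.01926) = 0.1368 / 0.04701 = 2.91

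**Rates, expected events (control v monitored) and two-sided Fisher rejection at 0.05.**

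| r | q | Rate, control v monitored | Events, 80 v 160 | Rejection | Events, 120 v 120 | Rejection |
|---|---|---|---|---|---|---|
| 20% | 25% | 0.57% v 1.14% | 0.46 v 1.82 | 0.2% | 0.68 v 1.36 | 0.1% |
| 20% | 50% | 0.76% v 1.94% | 0.60 v 3.10 | 0.4% | 0.91 v 2.32 | 1.3% |
| 20% | 75% | 0.94% v 2.74% | 0.75 v 4.38 | 1.7% | 1.13 v 3.28 | 4.3% |
| 30% | 25% | 0.86% v 1.70% | 0.68 v 2.73 | 0.4% | 1.03 v 2.04 | 0.7% |
| 30% | 50% | 1.13% v 2.90% | 0.91 v 4.65 | 2.0% | 1.36 v 3.48 | 4.4% |
| 30% | 75% | 1.41% v 4.10% | 1.13 v 6.57 | 7.5% | 1.69 v 4.92 | 11.3% |

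**Excess events in the monitored arm.** This is arm size × difference in rates. It runs from 120 × (0.01136 − 0.00570) = 0.7 to 160 × (0.04104 − 0.01410) = 4.3.

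The model sizes only unequal knowledge of AF. It sets q equal in the two arms, so any further tilt from unmasked adjudicators is not in these figures, and the documents give nothing to size it.

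**The case against.** The strongest reply is that the consequence is small and several links are inferred. Much of this stands.

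- **Size.** A reader might infer a 4.3-fold excess whatever the admission rate. The documents do not support that. It needs no admission ever to be labelled AF-related without prior known AF, and AF knowledge frozen at 30 days. Controls have an ECG at cardiology follow-up, typically 4-8 weeks after the MI (3.7), and 3.8 cites further AF over long-term follow-up.
- **Significance.** A reader might also infer that the trial would falsely show harm from monitoring. With a few events at most, rejection is 0.1-11% across the scenarios. All-cause hospitalization and death sit in the composite (3.6), and 4.8 has re-hospitalization compared by group, so a labelled excess can be checked against them.
- **Inferences.** Section 4.6 does not say that the committee judges AF-related hospitalization; that is the natural reading, since this outcome needs judgement. Section 3.7 does not name the telephone caller, although the call follows directly on the trainee's medication review. Reports go to the treating physicians; that an admitting team sees them is plausible but not stated. The follow-up form's line on reasons for re-hospitalization is only partly legible in the text available, so an AF tick-box cannot be ruled out. A tick-box would still not be a criterion.
- **Role overlap.** The arithmetic comes from unequal AF knowledge and would be the same with independent adjudicators. Section 4.3's technician read and masked review are real safeguards, but for recordings only.

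The core is untouched: there is no criterion, no masking of event adjudication is described, and the information available can differ by arm. If the committee does not judge this outcome, it is left without either a definition or an adjudicator.

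**Conclusion.** The point holds as a risk of differential labelling in one secondary outcome. As written, the plan lets arm and recorder-detected AF influence whether an admission counts as AF-related. With no true difference, the labelled rate would be about 2 to 3 times as high under monitoring (1.1-4.1% v 0.6-1.4%), with 4.3 as the upper bound for this mechanism. The AF rates are the plan's; the admission and labelling rates are assumed. In numbers this is roughly 1 to 4 excess events. The harm is a distorted estimate carried into the next trial. The documents do not support reading it as a likely false significant finding or as a threat to all-cause hospitalization or death. It should be settled before any event is judged, because a criterion chosen later by unmasked investigators would carry little weight.

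**What to change.** - **Section 3.6.** Count an admission as AF-related only if AF or flutter is documented on ECG or telemetry during that admission and is the main reason for it. A recorder history of AF alone is not sufficient.
- **Section 4.6.** State that the adjudicators judge AF-related hospitalization, re-infarction and stroke from packets prepared by existing research staff under a neutral linking code, with arm, the SpiderFlash report and references to it removed.
- **Reporting.** Give all-cause hospitalization by arm beside AF-related hospitalization.

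The cost is protocol wording and some coordinator time to redact a small number of records; no new assessor is needed. There are two downsides. Masking will be imperfect, because the trainee may recognise patients and anticoagulant use may remain visible; adjudicators who neither read recordings nor followed patients would mask better, at more cost. The criterion also narrows the outcome: some admissions for paroxysmal AF that has resolved by presentation will be lost, and the main reason for admission remains a judgement.
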